## **Intervention Components**

The intervention will be delivered using our four principal intervention modalities: (1) consumer-level wearable and scale (Fitbit Charge 3 and Aria Scale), (2) mobile text messages, (3) online social media pages and groups, and (4) individual health coaching (T1 only). Modalities will incorporate the theory-based behavioral change techniques (BCTs) and strategies for weight management (SWMs) mentioned in Table 1.

### Consumer-level wearable and scale: Fitbit Charge 3 and Aria Scale

**Figure 1.** Fitbit Charge 3

A Fitbit Charge 3 (<https://www.fitbit.com/charge3>) and Fitbit Aria 2 scale (<https://www.fitbit.com/aria2>) will be provided to all participants in the study. The Fitbit Charge 3 is not considered to be a medical device or a significant risk device. It is made of flexible, durable elastomer material similar to that used in many sport watches, and it has a surgical grade stainless steel buckle. It is lightweight (1.06 oz), 0.5 inches wide, and fits wrists that are 5.4 to 8.7 inches in diameter. It contains a triaxial accelerometer, an optical heart rate monitor, an altimeter, and a vibration motor.

All participants will have the ability to monitor physical activity, sleep and diet with the Fitbit Charge 3 and weight with the Aria scale. Additionally, participants in both intervention groups (T1 and T2) will receive feedback on physical activity, sleep, diet activity, and weight collected through these devices via SMS messaging, as described in the following section.

Data from the devices will be passively and securely streamed to the Fitbit website. It will then be retrieved using software developed by Small Step Labs, LLC and Fitabase Inc (<https://www.fitabase.com>) and stored securely on their servers. All data that is subsequently downloaded from Fitabase Inc. servers for analytic purposes will remain de-identified and will be stored on secure, password-protected CPHS/EPARC servers. There are two instances when researchers will contact Fitabase Inc. in order to delete data associated with participants in this study: 1) anytime that a participant chooses to withdraw from the study and 2) at the completion of the study (when all data analysis has been completed). Researchers will contact [name], CEO of Small Step Labs, LLC and creator of Fitabase ([[contact]](mailto:[contact])) and he will initiate a deletion of the data from live servers and all data will be phased out of offline backups within 90 days. After 90 days Small Step Labs will have no data associated with the study on their servers.

### SMS Component

Participants of both treatment groups (T1 and T2) will receive a behavioral weight loss messages through 1 to 2 tailored SMS daily. The messages will follow the same four-week format, detailed in Table 3, but will incorporate more advanced content and goals as the intervention progresses. This will be dependent on participants weight loss progress and progress in meeting weekly physical activity, dietary and sleep behavior goals. Tailored SMS messages will require participants to use all five core self-regulation strategies: self-monitoring, feedback on performance, behavioral intention formation, goal setting, and goal review.

**Table 3. Four-week schedule of text messages to be delivered in SMART 2.0 Intervention**

Week #	Sunday	Monday	Tuesday	Wednesday	Thursday	Friday	Saturday
1	Sleep Feedback & Sleep Tip	Exercise Feedback	Monthly Diet Feedback & Diet Tip	Weight Feedback & Weight Tip	Diet Tip	Mid-week Exercise Feedback & Exercise Tip	Resilience Tip
2	Sleep Feedback & Sleep Tip	Exercise Feedback	Diet Tips (2)	Weight Feedback & Weight Tip	Diet Tip	Mid-week Exercise Feedback & Exercise Tip	Resilience Tip
3	Sleep Feedback & Sleep Tip	Exercise Feedback	Mid-month Diet Feedback & Diet Tip	Weight Feedback & Weight Tip	Diet Tip	Mid-week Exercise Feedback & Exercise Tip	Resilience Tip
4	Sleep Feedback & Sleep Tip	Exercise Feedback	Diet Tips (2)	Weight Feedback & Weight Tip	Diet Tip	Mid-week Exercise Feedback & Exercise Tip	Resilience Tip

We will deliver SMS messaging using our previously developed text message system for weight loss and weight management. Based on data collected from a participant's use of Fitbit and Aria Scale, we will push tailored text messages from our SMS library (> 3000 messages). Messages will be time-based (e.g., occur at convenient time for participant every day) or data-based (e.g., in response to data collected from Fitbit and Aria). Most messages will be directly related to the participant's weekly weight, physical activity, caloric intake and sleep goals (tailored messages) and some will be general behavioral change strategies, depending on weekly behavioral goals. Messages based on weight, physical activity, caloric intake and sleep will be in response to data received from participants' use of Fitbit and Aria. For example, after weighing themselves, a message will be sent praising the participant for losing 2 pounds. Additionally, after a participant reaches a  $BMI < 25 \text{ kg/m}^2$  goals related to weight, caloric intake and physical activity will be automatically adjusted to reflect weight maintenance. For example, if a participant records a caloric intake that is equal to their caloric expenditure, their diet feedback will praise the participant and suggest continued caloric intake to maintain their healthy weight.

A sample of a week of text messages to the user are in Table 4. Participants will receive 1-2 messages each day and will be able to choose the timing of messages (e.g., mornings and evenings).

**Table 4. Example of weekly text messages to be used in SMART 2.0 intervention**

Day of the Week	Timestamp	Message Type	Message
Sunday	12pm	Sleep Feedback	You reached your weekly sleep goal by getting an average of 6 hrs 30 min a night. Keep it up and try to get in 6 hrs 50 min per night. Make sure to

			wear your Fitbit for at least 4 nights to get a better picture of your sleep patterns this week.
Sunday	7pm	Sleep Tip	Sleep tip: Try reading from a book or using a blue light filter on your laptop/phone when studying or reading before bedtime.
Monday	12pm	Exercise Feedback	Good work getting in 110 active minutes last week. But, your goal was to complete 140 minutes. Try to set a new goal of 130 minutes for this week. You can do it!
Tuesday	12pm	Diet Feedback	Terrific job tracking your calories this month. On average, you are eating as much as you burn. To lose 1 lb, you should be in a deficit of 500 calories per day. Continue to make progress by tracking consecutively for 3 days this month!
Tuesday	7pm	Diet Tip	When you're at the grocery store, make the healthiest choice by reading food labels and comparing calories per serving size. When in doubt, choose the option with less calories.
Wednesday	12pm	Weigh Reminder	Wednesday Weigh-day reminder! Time to step on the scale and see what progress you've made.
Wednesday	1pm	Weight Feedback	Great work! This week, you lost 1.5 lb(s). You got this! This week, your goal is to lose another 1-2 lbs.
Wednesday	7pm	Weight Loss Tip	A good way to stay away from food temptations is to be active. Next time you're craving something, go for a run or swim!
Thursday	12pm	Diet Tip	Eventually aim towards having only healthy items stored in your pantry and fridge! Do this by slowly getting rid of unhealthier items and replacing them with better-for-you alternatives.
Friday	12pm	Exercise Feedback	You're more than half way there! Good job getting to 90 active minutes so far. Your goal is to get 130 minutes by Monday, keep on going!
Friday	7pm	Fitness Tip	Do whatever makes exercise most enjoyable for you. Music? A podcast? You are much more likely to exercise consistently if you enjoy it.
Saturday	12pm	Resilience Tip	It's Saturday and time to release some stress! Press two fingers in the center of your other palm and hold for ten seconds.

### Online Group/ Social Media

After randomization, participants in T1 and T2 intervention-arms will be sorted by physical activity preference and placed in groups of 6 to 12 total participants through Facebook messenger. Current literature suggests that small, mixed-gender groups constructed based on a common characteristic (e.g. physical activity preference) result in improved outcomes in health interventions.

Each participant will “friend” the study health coach on Facebook, who will then add participants to their respective, private groups on Facebook Messenger. Content shared in the groups will only be accessible to the members of each group and the health coach. The health coach will post content and facilitate group discussion that follows a behavioral weight loss curriculum organized as a series of 24-week (6-month) cycles. Table 5 summarizes the content for the first 6-month cycle. Each subsequent cycle will follow the same format but will incorporate more advanced content and goals, dependent on group’s progress. Health coaches will also monitor all group interactions, respond to inquiries from participants, and elicit interactions using the following group-coaching methods:

1. *Mission statement formation:* Health coaches will work with group members at start of intervention (week 1) to establish ground rules and roles for participants and health coach. This mission statement will be revisited every 6-months and revised as necessary.
2. *Informational content and resources:* Health coaches will provide relevant informational content and resources applicable to the weekly curriculum topic as well as the group’s interests, recommendations

and goals. This includes, but is not limited to, local bike/running maps, healthy eating options on or near campus, recipes and exercise routines.

3. *Knowledge check-ins*: Health coaches will frequently assess group knowledge of weekly curriculum topics through polls and Q&A's. The intent is to give participants an opportunity to ask the health coaches questions relevant to weight loss and health behaviors.
4. *Shared experiences*: To elicit group cohesion and social support, health coaches will present open-ended questions designed to encourage participants to share their experiences with adopting and maintaining health behaviors and reaching personal weight loss goals. For example, a health coach may ask the group to share their favorite on-the-go healthy snack option.
5. *Goal-setting*: Through motivational interviewing techniques, health coaches will work with participants to create individual and group goals relating to the week's topic area and overall weight-loss goals. Additionally, health coaches will provide feedback on individual and group progress on meeting set goals.

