**6. SPECIFIC AIMS**

The primary aim of the study is to determine the efficacy of SMART 2.0 with technology and personal health coaching or with technology alone to improve objectively measured weight in kg over 24 months (96 weeks) compared to a control group.

Secondary aims will be to evaluate the following:

1. Anthropometric and physiological outcomes, physical activity, diet, sleep, self-esteem, body image, anxiety, depression, and the frequency and composition of participants' online communication about weight-related behaviors between groups at 6, 12, 18, and 24 months
2. The dose response (i.e., quantified engagement with technological modalities) of the intervention
3. The usability and acceptability of the intervention
4. Potential mediators and moderators of the intervention effects (e.g., social network connectivity, contamination, etc.)
5. Patterns of change in physical activity, diet, and sleep

Given that SMART 2.0 has been greatly enhanced by what we have learned from previous research, we hypothesize that both interventions will significantly improve weight compared to the control group, and the group receiving personal health coaching will experience the greatest improvement. We further hypothesize

that differences in secondary outcomes will favor the SMART 2.0 intervention groups. There is a critical need to advance our understanding of how to develop and deploy multimodal, technology-based weight-loss interventions that have the potential for long-term effects and widespread dissemination among young adults. SMART 2.0 is designed to maximize efficacy in a scalable manner. By measuring usability and acceptability, this study will inform intervention dissemination to campus wellness programs should the findings warrant it.

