## **8. RESEARCH DESIGN AND METHODS**

### **Overview**

The SMART 2.0 study is a 24-month (96 week) parallel-group randomized control trial designed to evaluate the efficacy of the intervention with technology and personal health coaching or with technology alone to improve objectively measured weight in kg over 24 months compared to a control group. We will recruit 642 overweight/obese young adults aged 18-35 at the University of California, San Diego (UCSD), San Diego State University (SDSU) and California State University, San Marcos (CSUSM) in San Diego. Participants will be assigned to one of three groups for a 24-month study period. The three groups include:

1. SMART 2.0 with technology, social media, and personal health coaching (T1)
2. SMART 2.0 with technology and social media alone (T2)
3. Control group

SMART 2.0 improves upon its predecessor by using a fully integrated system of modalities that includes 1) a popular consumer-level wearable activity tracker (Fitbit Charge 3), wireless scale (Aria Scale), and apps (Fitbit); 2) a highly tailored and interactive text messaging system (described in detail below); 3) multiple social media streams including Facebook, Facebook Messenger, Instagram and Twitter, and 4) enhanced social network mechanisms of influence. Consumer-level devices and apps will be used to self-monitor behavior, and their data will be passively acquired in real-time. Algorithms will be used to automatically deliver interactive text messages to support individually tailored goal setting, performance feedback, and goal review in a highly dynamic style that reflects participants' behavioral progress towards achieving a minimum goal of 5% weight loss. Participants will be encouraged to share their data and behavioral progress with others via social networking tools built into the apps. Social network mechanisms of influence will be used both within the study-space, to elicit participant-to-participant and health coach-to-participant support, as well as outside the study-space, to invoke social support and accountability from strong ties known to be important for long-term behavior change. Additionally, one group will receive monthly technology-mediated, real-time personal health coaching that is theory- and evidence-based.

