Subjects assigned to the SMART 2.0 with technology and personal health coaching treatment group (T1) will receive the following during the 24-month (96 week) intervention period: 1) Fitbit Charge 3 activity tracker and Aria scale, 2) daily text messages related to physical activity, diet, sleep and weight loss/maintenance, 3) access to SMART 2.0 social media pages and content through an online group with 6 to 12 participants total, and 4) technology-mediated, real-time individual health coaching. Subjects will receive 1 to 2 text messages on a daily basis, be asked to use their Fitbit on a daily basis and self-weigh using the Aria at least once per week, be asked to interact with their online group via social media as frequently as possible, and speak with their health coach at a predetermined session schedule.

Subjects assigned to the SMART 2.0 technology alone treatment group (T2) will receive the following activities during the 24-month (96 week) intervention period: 1) Fitbit Charge 3 activity tracker and Aria scale, 2) daily text messages related to physical activity, diet, sleep, resilience and weight loss/maintenance, and 3) access to SMART 2.0 social media pages and content through an online group with 12 participants total.

Subjects will receive 1 to 2 text messages on a daily basis, be asked to use their Fitbit on a daily basis and self-weigh using the Aria at least once per week, and be asked to interact with their online group via social media as frequently as possible.

Subjects assigned to the control group will simply receive a Fitbit Charge 3 and Aria scale to use at their discretion.

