### Health Coaching

Participants randomized into the T1 intervention arm will receive individual technology-mediated, real-time personal health coaching that is theory- and evidence-based. Health coaching sessions will consist of components of effective health coaching interventions including motivational interviewing (MI), participant determined behavioral goal setting, accountability for behaviors, and health education as part of an active learning process. Additionally, the health coach will utilize behavioral change techniques (BCTs) appropriate for individual coaching. These BCTs include goal setting (behavior and outcome), action planning, problem solving, feedback on behavior, social support and instruction on how to perform a behavior. All health coaches will have Master-level training in public health and at least two years' experience with individual health coaching. Sessions will last 10-15 minutes and will take place over the phone and/or through Google/Facetime/Skype/Zoom video-calls, depending on each participant's preference. Following each session, the health coach will send a session recap via e-mail that includes an outline of what was discussed, summary of behavioral and weight loss goals, and date/time of next session.

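### The arm that the primary aim calls technology alone includes coach-moderated group coaching, so its label and conclusion need changing; the plan should also say that online groups are formed within arm and settle their size

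*Combined protocol and SAP*

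**What the plan says.** **Label.** Section 6 (Specific Aims) sets out to test SMART 2.0 "with technology and personal health coaching or with technology alone to improve objectively measured weight in kg" against control. The Overview in section 8 repeats that label. Its arm list adds social media to the description of T2, but still says alone and does not mention a coach.

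**Content of T2.** The Online Group/ Social Media subsection applies to both intervention arms. A health coach adds participants to closed Messenger groups, posts material, leads discussion through weekly topics in repeated 24-week cycles, answers questions, and applies what the subsection itself calls group-coaching methods. Under goal-setting, with motivational interviewing techniques, "health coaches will work with participants to create individual and group goals relating to" the week's topic and weight loss. In addition, "health coaches will provide feedback on individual and group progress on meeting set goals". The Comparison Condition subsection counts contact between participant and coach among the things that both treatment arms receive and controls do not.

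**What only T1 receives.** The Health Coaching subsection gives T1 one-to-one sessions built on components "including motivational interviewing (MI), participant determined behavioral goal setting, accountability for behaviors" and health education. Standardizing Delivery of the Intervention prescribes 26 sessions in year one and 12 in year two.

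**Group formation and size.** After randomisation, "participants in T1 and T2 intervention-arms will be sorted by physical activity preference and placed in groups of 6 to 12 total participants". The Overview instead gives T1 groups of 6 to 12, and gives T2 "access to SMART 2.0 social media pages and content through an online group with 12 participants total".

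**Analysis.** Under Overall Approach, each intervention arm is compared with control at 24 months and the two p-values are adjusted by Holm's method. That T1 will do best is a hypothesis in section 6; no T1 versus T2 contrast is specified.

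**The concern.** The label and the content of T2 do not match. If T2 beats control, the aim's wording leads directly to the statement that technology by itself produced the weight loss. Section 6 says the study will inform dissemination to campus wellness programs if the findings warrant it. A program that took the aim at its word could plan without a coach, whereas the package tested includes coaches with master's-level public health training moderating groups throughout the intervention.

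A second, conditional concern is who shares a group with whom. The subsection on online groups names T1 and T2 together and sorts by activity preference, with no statement that sorting is done separately in each arm. If a T2 participant shared a thread with T1 members who are receiving one-to-one sessions, advice and motivation could pass between arms and narrow the T1-T2 difference.

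**Working it through.** No calculation decides this point. It rests on setting the sections side by side.

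**Step 1: what each arm receives** (Overview, Online Group/ Social Media, Health Coaching, Comparison Condition, Standardizing Delivery)

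| Component | T1 | T2 | Control |
|---|---|---|---|
| Activity tracker and scale | yes | yes | yes |
| Daily text messages | yes | yes | no |
| Study social media content | yes | yes | no |
| Online group moderated by a coach | yes | yes | no |
| Individual and group goals set with the coach in the group | yes | yes | no |
| Coach feedback on individual progress in the group | yes | yes | no |
| One-to-one sessions (26 + 12 = 38) | yes | no | no |

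The group curriculum runs in 24-week cycles. Over the 96-week intervention that is 96 / 24 = 4 cycles.

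**Step 2: what each difference means**

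- T2 minus control is the joint effect of texts, social media content and coach-moderated groups. The devices are common to both arms and drop out of the contrast, so coach contact is one of the few things that separates T2 from control.
- T1 minus T2, if groups are formed within arm, is the effect of one-to-one coaching added to that shared package.

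Neither difference isolates technology without a coach.

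**Step 3: are the groups within arm?**

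- The Online Group subsection names both arms together and is silent on separation.
- The Comparison Condition subsection reserves the groups for the two treatment arms jointly, so it shuts out controls only.
- The Overview gives a size for each arm, which points to within-arm groups without saying so.
- Under Engagement with Intervention Modalities, contamination is defined through control participants. Spill-over between T1 and T2 falls outside that definition.

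**Step 4: group size**

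| Section | T1 | T2 |
|---|---|---|
| Overview | 6 to 12 | 12 |
| Online Group/ Social Media | 6 to 12 | 6 to 12 |

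The two sections differ for T2. Arm-specific sizes presuppose separate groups, so mixing and differing sizes are alternative readings of the text.

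**Step 5: what the sample size covers**

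The plan's inputs are SD 4.92 kg, difference 1.60 kg, two-sided alpha 0.025 and 80% power.

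- Standardised difference: 1.60 / 4.92 = 0.325.
- A two-sample t-test needs 181.01, rounded up to 182 per group. This reproduces the plan; power at 182 is 0.802.
- Attrition: 182 / 0.85 = 214.1, stated as 214. Total: 3 x 214 = 642.

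This calculation serves the two comparisons with control and does not depend on what T2 is called. It makes no provision for T1 versus T2. As an illustration only, with 182 evaluable per arm, SD 4.92 kg and **assumed** T1-T2 differences:

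| Assumed difference (kg) | Power, alpha 0.025 | Power, alpha 0.05 |
|---|---|---|
| 1.6 | 0.80 | 0.87 |
| 1.2 | 0.53 | 0.64 |
| 0.8 | 0.24 | 0.34 |
| 0.4 | 0.07 | 0.12 |

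Because T1 and T2 share the coach-moderated groups, a difference below 1.6 kg is plausible, and power falls quickly there.

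**The case against.** The strongest reply is that T2 is described openly and the randomised comparison is sound. The Overview states that social network mechanisms are used to draw out support from the coach as well as from other participants. The background section counts remote contact with a coach among the technological modalities of the predecessor trial, so the team may intend technology to include it. What T1 alone receives is consistently called personal or individual coaching. Shared techniques are also not the same dose: T1 adds 38 scheduled sessions, while use of the groups is expected to vary. The plan measures communication with the coach and records the use of behavior change techniques.

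Most of this stands. T2 versus control is unbiased by its label, the coaching is not hidden, and T2 receives less of it than T1. What does not stand is the label: a reader of the aim, or of a conclusion that repeats it, would not learn that a coach set individual goals and gave individual feedback in T2. The arm list does not cure that.

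A reader might also infer more than the documents support:

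- **That neither comparison can be interpreted.** T2 versus control tests the package as delivered. T1 versus T2 is a hypothesis with no planned test and, with within-arm groups, still estimates the added effect of one-to-one coaching.
- **That the background trial of text messages sizes the problem.** Against control, messages alone gave 1.20% and messages plus coach calls 2.99%, a gap of 2.99 - 1.20 = 1.79 percentage points. This subtracts two separate comparisons with control, with no direct test or interval reported, and the coaching was by individual phone call. It says nothing about the effect of moderated group chat.
- **That the arms are mixed.** No section says so, and the Overview leans the other way.
- **That smaller groups would favour T1.** The plan credits small, mixed-gender groups built on a common characteristic. It does not rank 6 against 12, and 12 lies within the range given for both arms.

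**Conclusion.** The concern holds as a matter of labelling and interpretation. The primary aim misnames the package tested in one of the two primary comparisons, and all 214 participants planned for T2 are offered the coach-moderated component. A significant T2 result would support technology plus coach-moderated groups, and not technology alone. How much of any T2 effect comes from the coach cannot be derived from the documents, so no figure in kg is given. The conclusion assumes that the groups are delivered as the protocol describes; low uptake would reduce actual coach exposure but would not make the label accurate.

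The spill-over concern is conditional. It applies only if groups mix T1 and T2, which the text leaves open, and it bears on a hypothesised difference that has no planned contrast. The group-size point is limited to a disagreement between two sections that must be reconciled; no effect of size on outcome is claimed.

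**What to change.** 1. In section 6, in the Overview of section 8 and in the primary conclusion, name T2 *technology plus coach-moderated online groups*. Describe any T1-T2 difference as the added effect of one-to-one coaching, and label it exploratory unless a contrast is specified in Overall Approach.
2. In Online Group/ Social Media, state that every online group is formed within a single arm, with sorting by activity preference done within that arm.
3. Reconcile the Overview and Online Group/ Social Media on group size, so that T1 and T2 do not differ in it unintentionally.

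The cost is wording in the aims and conclusion and a sentence or two in the group procedures. The sample size and primary model are unchanged. The downsides are a less favourable claim for T2 and slightly less choice when matching participants on activity preference.
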